### **5.3 Screening and Eligibility**

The Investigator is responsible for keeping a record of all subjects who sign an Informed Consent Form for entry into the study. All subjects will be screened for eligibility. Screening procedures are outlined in Section 2, Schedule of Study Assessments. Unless otherwise specified, screening must take place within 28 days prior to initiation of therapy.

Approximately 45 subjects with previously untreated CLL/SLL will be screened for enrollment and must meet the eligibility criteria below.

#### **5.3.1 Inclusion Criteria**

Subjects must meet the following inclusion/exclusion criteria to be eligible for the study.

##### **Inclusion criteria**

1. Understand and voluntarily sign an informed consent form.
2. Age  $\geq 18$  years at the time of signing the informed consent form.
3. Able to adhere to the study visit schedule and other protocol requirements.
4. Patients must have histologically or cytologically confirmed CD5+/CD20+ B-Cell chronic lymphocytic leukemia or small lymphocytic lymphoma. The diagnosis of CLL is based upon the NCCN guidelines. Any outside pathology slides used as inclusion criteria for the patient will be reviewed at this institution to confirm the

diagnosis. The patient must meet all of the following CLL criteria to participate in this study:

- absolute lymphocyte count  $> 5000/\mu\text{L}$
- CD20+ and CD5+
- Bone marrow lymphocytes  $\geq 30\%$
- Or previous confirmed diagnosis of CLL/SLL with less than  $5000/\mu\text{l}$  or less than 30% lymphocytes in BM

5. Patients are eligible if they have stage III or IV disease. Patients with stage 0, I or II disease will be eligible if they have evidence of active disease defined as one or more of the following signs/symptoms: (See also Appendix E: Criteria for Treatment)

- Documented weight loss of  $\geq 10\%$  over a six month period
- Febrile episodes of 38 degrees Celsius (100.5 degrees F) or greater for greater than 2 weeks without evidence of infection
- Massive or progressive splenomegaly defined as  $> 6$  cm below the left costal margin
- Massive ( $> 10$  cm in longest diameter) or progressive lymphadenopathy.

6. Patient has not received any prior treatment for CLL in the past.

7. ECOG performance status of  $\leq 2$  at study entry (see Appendix B).

8. Laboratory test results within these ranges:

- Absolute neutrophil count  $\geq 1000/\text{mm}^3$
- Platelet count  $\geq 50,000/\text{mm}^3$

*(Adequate baseline platelet and neutrophil levels must be present, unless there is clear evidence of extensive bone marrow involvement with tumor infiltration  
Extensive bone marrow involvement is defined as:*

*-Bone marrow lymphocytes  $\geq 30\%$*

---

- Renal function assessed by calculated creatinine clearance  $\geq$  30ml/min by Cockcroft-Gault formula. (see Appendix: Cockcroft-Gault estimation of CrCl)
- Total bilirubin  $\leq$  1.5 x ULN
- AST (SGOT) and ALT (SGPT)  $\leq$  2.5 x ULN.
- Alkaline phosphatase  $<2.5$  x ULN

9. Disease free of prior malignancies for  $\geq$  5 years with exception of currently treated basal cell, squamous cell carcinoma of the skin, or carcinoma "in situ" of the cervix or breast.

10. All study participants must be registered into the mandatory REMS® program, and be willing and able to comply with the requirements of REMS®.

11. Females of childbearing potential (FCBP)† must have a negative serum or urine pregnancy test with a sensitivity of at least 50 mIU/mL within 10 – 14 days and again within 24 hours prior to prescribing lenalidomide for Cycle 1 (prescriptions must be filled within 7 days) and must either commit to continued abstinence from heterosexual intercourse or begin TWO acceptable methods of birth control, one highly effective method and one additional effective method AT THE SAME TIME, at least 28 days before she starts taking lenalidomide. FCBP must also agree to ongoing pregnancy testing. Men must agree to use a latex condom during sexual contact with a FCBP even if they have had a successful vasectomy. See Appendix A: Risks of Fetal Exposure, Pregnancy Testing Guidelines and Acceptable Birth Control Methods.

---

† A female of childbearing potential is a sexually mature female who: 1) has not undergone a hysterectomy or bilateral oophorectomy; or 2) has not been naturally postmenopausal for at least 24 consecutive months (i.e., has had menses at any time in the preceding 24 consecutive months).

---

12. Able to take aspirin (81 or 325 mg) daily as prophylactic anticoagulation (patients intolerant to ASA may use warfarin or low molecular weight heparin).

### **5.3.2 Exclusion criteria**

1. Any serious medical condition, laboratory abnormality, or psychiatric illness that would prevent the subject from signing the informed consent form.
2. Pregnant or breast feeding females. (Lactating females must agree not to breast feed while taking lenalidomide).
3. Any condition, including the presence of laboratory abnormalities, which places the subject at unacceptable risk if he/she were to participate in the study or confounds the ability to interpret data from the study.
4. Evidence of laboratory TLS by Cairo-Bishop Definition of Tumor Lysis Syndrome (see Appendix H). Subjects may be enrolled upon correction of electrolyte abnormalities.
5. Use of any other experimental drug or therapy within 28 days of baseline.
6. Known hypersensitivity to thalidomide.
7. The development of erythema nodosum if characterized by a desquamating rash while taking thalidomide or similar drugs.
8. Any prior use of lenalidomide.
9. Concurrent use of other anti-cancer agents or treatments.
10. Known seropositive for or active viral infection with human immunodeficiency virus (HIV)
11. Positive serology for hepatitis B (HB) defined as a positive test for HBsAg. In addition, if negative for HBsAg but HBcAb positive and HBsAb negative, a HB DNA test will be performed and if positive the subject will be excluded. Note: If HBcAb positive and HBsAb positive, which is indicative of a past infection, the subject can be included. Patients who are seropositive because of hepatitis B virus vaccine are eligible. Consult with a physician experienced in care &

management of subjects with hepatitis B to manage/treat subjects who are anti-HBc positive

12. Positive serology for hepatitis C (HC) defined as a positive test for HCAb, in which case reflexively perform a HC RIBA immunoblot assay on the same sample to confirm the result
13. Subjects who have current active hepatic or biliary disease (with exception of patients with Gilbert's syndrome, asymptomatic gallstones, liver metastases or stable chronic liver disease per investigator assessment) are ineligible.
14. Chronic or current infectious disease requiring systemic antibiotics, antifungal, or antiviral treatment such as, but not limited to, chronic renal infection, chronic chest infection with bronchiectasis, tuberculosis and active Hepatitis C.
15. History of significant cerebrovascular disease in the past 6 months or ongoing event with active symptoms or sequelae
16. Clinically significant cardiac disease including unstable angina, acute myocardial infarction within six months prior to randomization, congestive heart failure (NYHA III-IV), and arrhythmia unless controlled by therapy, with the exception of extra systoles or minor conduction abnormalities.
17. Significant concurrent, uncontrolled medical condition including, but not limited to, renal, hepatic, gastrointestinal, endocrine, pulmonary, neurological, cerebral or psychiatric disease which in the opinion of the investigator may represent a risk for the patient.

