## 2 Schedule of Study Assessments \*

Procedure	All visits/assessments may be scheduled $\pm$ 3 business days										
	Screening  <math>\leq</math> 28 days from Baseline (First day drug administration)	Cycle 1	Cycles 2 - 3	Cycle 4 				Cycles 5-12	Lenalidomide Maintenance Therapy	Discontinuation From Protocol Therapy 	Follow- Up Phase
	Days 1, 8, 15, and 22	Days 1, and 15	Day 1	Day 3 or 4 at investigator discretion	Day 8	Day 15	Day 22	Day 1 and 15			
Study drug administration **		X	X	X					X	X	
Record prior medications, treatments	X										
Record prior anti-cancer therapies	X										
Physical examination, vital signs, weight	X	X 	X 	X 					X 		
ECOG performance status	X	X 	X 	X 					X 		
ECG	X										
Assess lymphadenopathy, spleen / liver 		X 	X 	X 		X 	X 		X 		
Peripheral blood for , ZAP 70, $\beta$ -2 microglobulin, and IgHV mutational status 	X										
Research samples 	X			X							
Baseline lesion assessment	X			X							
Bone marrow 	X			X					X	X	X 
CT of the neck, chest, abdomen & pelvis 	X			X					X		X 
Hematology 	X	X	X	X 		X 	X 	X 	X 	X 	
Serum chemistry 	X	X	X	X 	X 	X 	X 	X 	X 	X 	
Hepatitis B and C serology, HBV DNA PCR 	X 										
Pregnancy testing 	X			X		X	X	X	X		
Register patient into REMS® program	X										

Prescribe lenalidomide via REMS 				X				X			
Record adverse events 		X	X	X				X	X 		
Record concomitant therapies/procedures		X	X	X				X			
Obtain Follow-Up anti-cancer treatments											X
Obtain Follow-Up survival information											X

\* An unscheduled visit can occur at any time during the study. Source must be maintained for these unscheduled visits. The date for the visit and any data generated must be recorded on the appropriate CRF. Source documents for these unscheduled visits must also be maintained.

\*\* See Table 1 for detailed study drug administration schedule.

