 Chemistry includes sodium, potassium, chloride, CO2, calcium, magnesium, phosphorus, BUN, creatinine, glucose, albumin, total protein, alkaline phosphatase, total bilirubin, AST/SGOT, ALT/SGPT, LDH, and uric acid. At a minimum, for tumor lysis syndrome (TLS) monitoring purposes, subjects will have chemistry assessments weekly during at least the first 2 cycles of lenalidomide-containing treatment. Chemistry assessments on Day 3 or 4 of Cycle 1 of lenalidomide-containing treatment are at the investigator's discretion. In addition, because the risk for TLS may be elevated when lenalidomide is re-started after treatment interruptions or when the lenalidomide dose is escalated, in any cycle in which the lenalidomide dose is escalated or re-escalated or treatment is interrupted for more than 1 week, subjects may need to have weekly chemistry assessments performed for at least 4 consecutive weeks as well as an additional chemistry assessment on day 3 or 4 during the first week of escalating, re-escalating or re-initiating lenalidomide therapy. If TLS occurs, subjects will have additional chemistry assessments weekly for at least 4 consecutive weeks as well as on Day 3 or Day 4 following re-initiation of lenalidomide. For subjects who do not experience any abnormalities in serum chemistry assessments for 2 consecutive cycles while on a stable lenalidomide dose (without dose escalation or interruption of the planned dosing schedule) throughout these 2 cycles, the timing of chemistry assessments may be reduced to Day 1 and Day 15 in subsequent cycles. See section 5.6.1.1 for TLS prophylaxis instructions. To include Thyroid Stimulating Hormone (TSH) at Screening, at treatment discontinuation, and whenever clinically indicated. T3 and T4 levels may be assessed as clinically indicated.

 Hepatitis B Virus DNA by PCR will be tested at screening. If it is positive then it will be tested every 2 weeks during cycle 1, every 4 weeks during cycles 2 ad 3, and then every 2 to 3 months thereafter.

---

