### **3.2.2 Ofatumumab Adverse Events**

During clinical trials of ofatumumab in FL, CLL and RA subjects, adverse events occurring during the infusions of trial drug have been reported. The following reactions should be regarded as expected infusion-related adverse reactions in connection with the use of ofatumumab probably as a consequence of B cell depletion and cytokine release: pruritus, dyspnea, bronchospasm, throat irritation, cough, pharyngolaryngeal pain, flushing, hyperhidrosis, nausea and vomiting, abdominal pain, hypotension, rash/urticaria, influenza-like-illness, fatigue, fever, chills, headache, dizziness, myalgia and arthralgia.

The incidence of infusion-related symptoms was highest during the first infusion and decreased substantially with subsequent infusions. Implementation of pre-medication before infusions has reduced the number as well as the severity of infusion related adverse events. One serious case of cytokine release complicated with laryngeal edema and one case of anaphylactoid-like reaction have been observed; both events were fully reversible after cessation of the infusion and proper treatment. It should be noted that none of these subjects received premedication with prednisolone.

During the ongoing study in subjects with CLL refractory to alemtuzumab and fludarabine, infusion related adverse events have been reported in approximately 30% of subjects. Only 2-3 % were serious adverse events. All subjects received pre-medication with prednisolone, acetaminophen and antihistamine. In the completed CLL trial 402 in patients with relapsed or refractory CLL, 15% of the subjects had serious infections. In the ongoing CLL 406 trial in subjects refractory to both alemtuzumab and fludarabine an increased frequency of serious infections (25-30%) have been reported.

---

Subjects who are HBsAg negative, anti-HBc positive and HBV DNA negative may be included in the study but must undergo HBV DNA monitoring. Consult with a physician experienced in care & management of subjects with hepatitis B to manage/treat subjects who are anti-HBc positive. Initiate anti-viral therapy if required. If a subject's HBV DNA becomes positive during the study, notify the NOVARTIS medical monitor. For subjects who have not completed planned ofatumumab therapy, discuss with the medical monitor the risks and benefits of continuing or discontinuing ofatumumab before appropriate treatment decisions are made for that individual subject.

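### Exclusion 11 sets no HBV DNA condition for patients positive for both HBcAb and HBsAb, so a DNA-positive patient passes the hepatitis B criterion

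*Combined protocol and SAP*

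**What the plan says.** Section 5.3 tells the investigator that subjects "must meet the eligibility criteria below". Within those criteria, exclusion 11 (section 5.3.2) treats hepatitis B in three steps:

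- HBsAg positive: excluded.
- HBsAg negative, with "HBcAb positive and HBsAb negative, a HB DNA test will be performed and if positive the subject will be excluded".
- A note for the remaining HBcAb-positive patients: "If HBcAb positive and HBsAb positive, which is indicative of a past infection, the subject can be included". No DNA result is mentioned. A further sentence advises consulting a physician experienced in hepatitis B about managing or treating anti-HBc-positive subjects.

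Section 3.2.2 (Ofatumumab Adverse Events) states entry differently, without reference to HBsAb: "Subjects who are HBsAg negative, anti-HBc positive and HBV DNA negative may be included in the study but must undergo HBV DNA monitoring". For conversion on study it adds that if a subject's "HBV DNA becomes positive during the study, notify the NOVARTIS medical monitor". The risks and benefits of continuing or stopping ofatumumab must then be discussed with that monitor before treatment decisions are made.

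The Schedule of Study Assessments (section 2) lists "Hepatitis B and C serology, HBV DNA PCR" in the screening column. Footnote 7 says "Hepatitis B Virus DNA by PCR will be tested at screening", and continues: "If it is positive then it will be tested every 2 weeks during cycle 1", then every 4 weeks in cycles 2 and 3, and every 2 to 3 months after that.

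**The concern.** The screening PCR result is known before the first dose, and the plan already treats detectable HBV DNA as a reason to exclude a patient whose HBsAb is negative. For an HBsAb-positive patient the same result has no stated effect on entry.

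This is a safety matter. The patient would receive eight ofatumumab infusions, each with 1 g/m² methylprednisolone, in cycles 1 to 3, and could go on to four more infusions with lenalidomide. Section 3.2.2 regards DNA turning positive during the study as serious enough to involve the medical monitor. A patient who is already positive at screening does not convert on study, so that step is not triggered. Entry then depends on the investigator's judgement.

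**Working it through.** The main check is a comparison of texts; the plan has no figure of its own to reproduce.

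**Step 1. Entry rules side by side.** For HBsAg-negative, HBcAb-positive patients, HBsAb and HBV DNA give four combinations.

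| HBsAb | HBV DNA | Exclusion 11 | Section 3.2.2 | Agree? |
|---|---|---|---|---|
| Negative | Negative | Not excluded | Includable, with monitoring | Yes |
| Negative | Positive | Excluded | Not named as includable | Yes |
| Positive | Negative | Includable | Includable, with monitoring | Yes |
| Positive | Positive | Includable | Not named as includable | **No** |

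**Step 2. Does footnote 7 settle it?** No. A positive screening PCR leads to repeat tests during treatment. Exclusion 11 has already removed HBsAg-positive patients and HBsAb-negative, DNA-positive patients. Among HBcAb-positive patients, then, the on-treatment schedule can apply only to the last row of the table, so the footnote presupposes that such a patient is treated. The group that section 3.2.2 says must be monitored, anti-HBc positive and DNA negative, has no timetable in the footnote.

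**Step 3. Do other criteria settle it?** None names HBV DNA for this subgroup.

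- Exclusion 3 depends on a finding of unacceptable risk.
- Exclusion 13 exempts stable chronic liver disease.
- Exclusion 14 applies only where the infection needs systemic treatment; its hepatitis example is active hepatitis C.
- Exclusion 17 rests on the investigator's opinion.
- Inclusion 8 is met with AST and ALT up to 2.5 × ULN.

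**Step 4. How often could it happen?** The documents give no prevalences, so these inputs are assumptions: a = proportion anti-HBc positive, 2% to 10% (0.9 to 4.5 of 45, about 1 to 5 patients); b = proportion of those HBsAb positive, 50% to 90%; c = proportion of those DNA positive, 1% to 10%. The sample size of 45 is from section 10.2.

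Per-patient probability p = a × b × c. Expected number = 45p. Chance of at least one = 1 − (1 − p)^45.

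| Case | p | Expected of 45 | Chance of at least one |
|---|---|---|---|
| Low | 0.02 × 0.5 × 0.01 = 0.0001 | 0.0045 | 0.0045 |
| Middle | 0.05 × 0.7 × 0.05 = 0.00175 | 0.079 | 0.076 |
| High | 0.10 × 0.9 × 0.10 = 0.009 | 0.405 | 0.334 |

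**Step 5. Testing load if footnote 7's intervals are applied to DNA-negative patients.** Cycle 1: 28/14 = 2 PCRs. Cycles 2 and 3: 56/28 = 2. Cycles 4 to 12: 9 × 28 = 252 days, or 2 to 4 PCRs at intervals of 3 to 2 months. The total is 6 to 8 per patient through cycle 12. For 1 to 5 patients that is 1 × 6 = 6 to 5 × 8 = 40.

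**The case against.** The strongest reply is that section 3.2.2 is permissive. It says who may enter and does not write that only they may. Read strictly, it is silent on the disputed combination and contradicts nothing. Read as a condition of entry, it means the protocol already requires DNA negativity and exclusion 11 merely fails to repeat it. Section 5.3 states no precedence over section 3.2.2. The first point stands as a matter of wording. But a sentence that lists DNA negativity among the features of includable patients is most naturally read as setting a condition, and on either reading the criterion used for screening does not carry it.

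Second, there are safeguards. A positive PCR is a laboratory abnormality that exclusion 3 could catch, a patient needing antivirals falls under exclusion 14, specialist consultation is advised, and footnote 7 repeats the PCR. These make unexamined entry less likely. They remain discretionary or conditional, however, and the note in exclusion 11 gives specific permission to enrol. What is missing is an explicit bar, or a medical-monitor discussion before entry.

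Third, exclusion 11 gives its reason for the split: the double-positive pattern indicates past infection. That supports treating the serology differently, but it does not explain disregarding a DNA result that points the other way.

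Fourth, the case is rare and its frequency is wholly assumed; in the middle case there is about a 92% chance that nobody falls in it. That is right, and it limits the weight of the point.

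**Conclusion.** The concern holds. Exclusion 11 lets an HBcAb-positive, HBsAb-positive patient with detectable HBV DNA at screening pass the hepatitis B criterion, whereas section 3.2.2 names only DNA-negative anti-HBc-positive patients as includable. The schedule does not resolve the difference, and no other criterion does so explicitly.

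The gap is narrow: one combination of four, with an expected 0.005 to 0.4 patients among 45 under the assumed prevalences. It does not touch the two-stage design, its error rates or its sample size. It deserves correction because the hazard is foreseeable, the result is available before dosing, and the change is cheap.

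Two limits apply. The conclusion reads section 3.2.2 as setting a condition, which its wording suggests but does not state outright. And the documents do not say whether accrual was still open at Amendment 5. If it had closed, the entry change would have little effect, but the monitoring correction would still matter for anyone on treatment.

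**What to change.** 1. Reword the note in exclusion 11, for example: *A patient with both HBcAb and HBsAb positive may enter only with a negative HBV DNA PCR at screening.* Every anti-HBc-positive patient with detectable DNA is then excluded, whatever the HBsAb result.
2. Reword footnote 7 so that a positive screening PCR means exclusion, and the repeat-test schedule applies to enrolled anti-HBc-positive, DNA-negative patients.

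**Cost.** The entry change is amendment wording only and adds no screening test. On the assumed prevalences, at most about one patient becomes ineligible. The monitoring change means about 6 to 8 PCRs per affected patient through cycle 12, or roughly 6 to 40 in all, and more for those who continue lenalidomide beyond cycle 12 if the schedule carries on. Section 3.2.2 already requires this monitoring but sets no interval; the rewording supplies one.

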#### **5.4 Visit schedule and assessments**

Screening Assessments and all on study scheduled visits and assessments are outlined in Section 2: Table of Study Assessments.

Research samples for storage will be drawn during screening, day 1 of cycle 4, day 1 of Maintenance Therapy (or at time of discontinuation therapy if earlier than cycle 12). At each timepoint the following tubes will be obtained: three 10 ml green tops and one 10 ml

Amendment 5 Dated 03/02/2016

---

plain red top tube. The samples will be stored in the Moffitt Cancer Center laboratory of [name] for examining sample phenotypics and analysis of functionality of T-cell sub-populations. At treatment discontinuation, subjects will undergo off study evaluations per the Schedule of Assessments, Section 2. Study subjects who have completed the 12 cycles of treatment protocol, have not progressed while on therapy, and do not continue on lenalidomide maintenance therapy (MT) will be followed every 6 months for survival until disease progression, study closure, withdrawal of consent, or death. Subjects who progress while on MT and discontinue treatment will do the end of treatment testing. If the bone marrow biopsy and CT scans have been performed in the past 28 days to determine progression of disease, it is not necessary to repeat these tests.

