### **5.8 Lenalidomide Maintenance Therapy (MT)**

Per protocol Section 5.5, subjects who do not achieve a CR by Cycle 12 may continue lenalidomide single agent until disease progression or unacceptable toxicities. Any subject completing 12 cycles of protocol therapy may begin Lenalidomide Maintenance Therapy (MT).

During MT the following study procedures will be initiated:

1. The subject will have a safety CBC with differential and CMP every four weeks which will not be recorded in the database.
2. Physical examinations will be at the discretion of the investigator or per standard of care. The physical exam results will not be recorded in the database.
3. For the purpose of the study, vital signs, weight, and concomitant medications are not required to be recorded in the database.
4. No subject pill diary or source documentation of dosing will be maintained. The patient report of daily dosing will be sufficient to document adherence.
5. The only adverse events collected and entered into the database will be grade 3 or grade 4 cytopenias.
6. All standard of care guidelines as outlined by the Celgene Corporation for lenalidomide administration, including prophylactic anticoagulation, pregnancy prevention, and counseling through the Revlimid REMS program will continue to be followed.
7. Serious adverse events will be collected and reported as outlined in section 6.
8. A bone marrow biopsy and CT scan will be performed every six months for two years. After this time point, these tests need only be performed at the discretion of the treating physician.

At the discretion of the investigator:

Amendment 5 Dated 03/02/2016

---

1. Lenalidomide dose may be maintained at the subject's current dose or if previously dose reduced, may be escalated to the maximum of 10 mg daily.
2. Lenalidomide dose reductions may be initiated to 5 mg daily or 5 mg every other day.

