### **5.9 Follow-Up**

If a subject discontinues study treatment at any time during cycles 1-12, “Discontinuation from Protocol Therapy” on the Schedule of Assessments, Section 2 will be performed. If the bone marrow biopsy and CT scans have been performed in the past 28 days to determine progression of disease, it is not necessary to repeat them.

The subject will then enter the follow-up period unless consent is withdrawn. If a subject enters Maintenance Therapy (MT) after cycle 12, the follow-up period will begin after discontinuation of lenalidomide in MT. If a subject completes 12 cycles and does not enter MT, follow-up will begin at the completion of cycle 12.

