#### **6.2.4 Time Period and Frequency of Detecting and SAEs**

Once an investigator determines that an event meets the protocol definition of an SAE, the SAE will be reported to Novartis within 24 hours of being notified of the event. All SAEs regardless of relationship to investigational product will be collected from the first dose of investigational product to after the last dose of investigational product (minimum of 6 months or until the end of the follow-up period which ever is longer). All SAEs regardless of causality will be collected until the end of the follow-up period.

Amendment 5 Dated 03/02/2016

---

From the time a subject consents to participate in and completes the study all SAEs assessed as related to study participation (e.g., protocol-mandated procedures, invasive tests, or change in existing therapy) or related to NOVARTIS concomitant medication, will be reported promptly to NOVARTIS.

Any SAE brought to the investigator's attention after the subject has completed the study and considered by the investigator as possibly related to investigational product must be reported to NOVARTIS.

This includes serious, related, not related, labeled (expected) and, unlabeled (unexpected) adverse experiences. All deaths during treatment or within 30 days following completion of active protocol therapy must be reported within 24 hours.

Any SAEs experienced after the follow-up period should only be reported to Novartis if the investigator suspects a causal relationship to the study drug. Recurrent episodes, complications, or progression of the initial SAE must be reported as follow-up to the original episode within 24 hours of the investigator receiving the follow-up information. A SAE occurring at a different time interval or otherwise considered completely unrelated to a previously reported one should be reported separately as a new event. The end date of the first event must be provided.

The original copy of the SAE Report and the fax confirmation sheet must be kept within the Trial Master File at the study site.

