# **9 Data Management**

## **9.1 Analyses and Reporting**

Data will be analyzed and reported after completion of treatment protocol. All subsequent data collected will be analyzed and reported in a follow-up clinical report.

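### Section 5.4 stops survival follow-up at progression for 12-cycle completers off maintenance, while 5.9 and Section 2 state no stop; if 5.4 is followed, overall survival is likely to be overstated

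*Combined protocol and SAP*

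**What the plan says.** Section 5.4 covers patients who complete the 12 cycles, have not progressed on therapy and do not go on to lenalidomide maintenance. They "will be followed every 6 months for survival until disease progression, study closure, withdrawal of consent, or death".

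Section 5.9 deals with the same patients: "If a subject completes 12 cycles and does not enter MT, follow-up will begin at the completion of cycle 12". It names no end at progression. For patients who stop treatment during cycles 1-12, it says "The subject will then enter the follow-up period unless consent is withdrawn". For maintenance patients, follow-up starts once lenalidomide is stopped.

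In the Section 2 table, the Follow-Up Phase has two rows of its own, "Obtain Follow-Up survival information" and "Obtain Follow-Up anti-cancer treatments", neither with a stop at progression.

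Section 5.1, describing the response assessment after cycle 3, says that patients who have progressed are taken off the study. It does not say whether that covers survival follow-up as well as treatment.

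Section 10.4 makes OS a secondary endpoint, summarised by Kaplan-Meier and reported descriptively. Its only censoring sentence is written for patients lost or dropping out before their response evaluation.

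**The concern.** Progression is an event for progression-free survival but not for OS. Section 5.4 nevertheless lets it end the contact whose stated purpose is survival. A patient who has just progressed is usually at higher risk of death than one who has not, so censoring OS at that moment is informative. Those who remain at risk are healthier than those who left, and the Kaplan-Meier curve drifts upward.

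The same event also has opposite effects within one cohort. Under 5.7 and 5.9, progression during cycles 1-12 or on maintenance ends treatment and leads into follow-up. Under 5.4, progression in a completer off maintenance ends follow-up.

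At stake is one of the two named secondary endpoints. Deaths that were never collected cannot be restored by analysis.

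**Working it through.** **Reading the sections together.** For completers off maintenance, 5.4 gives an explicit stop at progression. Section 5.9 gives a start and no stop. Section 2 lists survival and later anti-cancer treatment with no stop, and the second item would largely go uncollected if contact ended at progression. The conflict is therefore an explicit stop against silence, with Section 2 pointing towards contact after progression.

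**Size.** The documents state no OS rate, event count or OS precision, so there is no plan figure to reproduce. I used an illness-death model with constant hazards and assumed inputs:

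- median time to progression 24, 36 or 48 months, hazard λ = ln 2 / median;
- median time to death without progression 120 or 240 months, hazard μ;
- median survival after progression 12, 24, 36 or 48 months, hazard ν;
- share s of event-free completers who are off maintenance: 10, 25, 50 or 75%.

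Cycle 12 ends at 12 × 28 = 336 days, or 11.0 months. From then on, in the off-maintenance group, a progression is found at the next 6-monthly contact and the patient leaves the OS risk set. All other patients are followed to death.

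True survival is S(t) = e^(−(λ+μ)t) + [λ/(λ+μ−ν)] × [e^(−νt) − e^(−(λ+μ)t)].

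The Kaplan-Meier limit is exp(−∫h), where h = [μ × (event-free) + ν × (progressed and still followed)] / (all still followed). The bias is this limit minus S(t).

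**Worked example** (medians 36, 240 and 24 months, s = 50%). λ = 0.01925, μ = 0.00289, ν = 0.02888 per month. At 36 months, e^(−(λ+μ)t) = 0.4506, e^(−νt) = 0.3536 and λ/(λ+μ−ν) = −2.857. So S = 0.4506 + 2.857 × (0.4506 − 0.3536) = 0.728.

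| | 24 months | 36 months |
|---|---|---|
| True OS | 83.9% | 72.8% |
| Kaplan-Meier under 5.4 | 84.4% | 74.8% |
| Bias, points | 0.5 | 2.0 |

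**Full grid** (3 × 2 × 4 × 4 = 96 scenarios), bias in points:

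| | 24 months | 36 months |
|---|---|---|
| Range | 0.0 to 1.8 | 0.1 to 5.9 |
| Median | 0.3 | 1.0 |
| s = 25% | 0.1 to 0.6 | 0.3 to 1.7 |
| s = 75% | 0.2 to 1.8 | 1.0 to 5.9 |
| Maximum if post-progression median is at least 24 months | 0.9 | 3.4 |

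The 24-month bias is small because the first contact that can remove anyone comes at 11.0 + 6 = 17.0 months.

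**Null check.** With equal hazards (both death medians 48 months) the bias is 0.0 at every time.

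**Scale.** With 45 patients fully followed, the binomial standard error in the worked example is √(0.839 × 0.161 / 45) = 5.5 points at 24 months and √(0.728 × 0.272 / 45) = 6.6 at 36.

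**Why these horizons.** The synopsis gives a study duration of 2 years. Maintenance assessments run for two years after cycle 12, to 11.0 + 24 = 35 months. Section 9.1 adds a later report: "All subsequent data collected will be analyzed and reported in a follow-up clinical report".

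**The case against.** The strongest reply is that 5.4 opens by referring the reader to Section 2 for visits and assessments, and Section 2 has no stop. A site working from the table would collect these deaths, and there would be no bias. That is a fair reading, and it is why the conclusion is conditional. But 5.4 is the only place that states when survival follow-up ends for this group, so staff could reasonably act on it.

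Deaths might also be caught as serious adverse events. Section 6.2.4 says "All SAEs regardless of causality will be collected until the end of the follow-up period", with a 6-month minimum. That period could end under the same 5.4 rule, so it is not a dependable backup.

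The magnitude rests wholly on assumed values, and that objection stands. The top of the range needs 75% of completers off maintenance, although 5.5.3.3 and 5.8 open maintenance widely. It also needs a 12-month median survival after progression. That is shorter than the 13.7 and 15.4 months of overall survival the protocol reports for fludarabine-refractory patients, so the range without that value deserves more weight. The typical bias is well below the standard error with 45 patients.

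Three stronger readings do not hold:

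- A reader might infer that survival follow-up stops at progression for everyone. The 5.4 stop names one subgroup, and 5.9 places other patients in follow-up. Section 5.1 does leave early progressors unclear, so the contrast between groups is not settled either.
- A reader might infer that progression-free survival is also biased, because the footnotes fix 6-monthly CT and marrow only during maintenance. The Section 2 table, as it reads here, also marks both in the Follow-Up Phase, and 10.4 does not prescribe censoring at the last scan.
- A reader might project much larger distortions at five years. The documents set no such horizon and give no date for the follow-up report.

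**Conclusion.** The concern holds in conditional form. If 5.4 is followed as written, OS is censored at a prognostic event in completers off maintenance, and the estimate is too high whenever the death hazard rises after progression. Under the stated assumptions, with every progression found at the next contact, the bias is negligible to small at 2 years and modest at 3 years. It grows only in later reports. In the worked example, and through most of the grid, it lies within sampling error. Unlike sampling error, though, it always runs in the favourable direction when the hazard rises.

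The model takes all other patients as followed to death, which depends on how 5.1 is resolved. The subgroup's size is unknown. No decision in the plan uses OS: the response endpoint and the 26/45 two-stage rule are untouched. It is still worth correcting, because the sections disagree and the remedy is simple.

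**What to change.** - **Section 5.4:** delete progression from the list of events that end survival follow-up.
- **Sections 5.1, 5.4, 5.9 and 2:** state one rule, that all treated patients are followed for survival every 6 months until death, withdrawal of consent or study closure. Make clear that removal at progression in 5.1 refers to treatment and not to survival follow-up.
- **Section 10.4:** censor OS at the date last known alive, for all patients without a recorded death.
- **Patients already stopped under 5.4:** update vital status once before the OS analysis, consent permitting.

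The cost is the wording change and a phone or chart check every 6 months after progression. No procedure is added. OS may look less favourable than it would under 5.4.
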